3.1.3 Definition of Baseline

Baseline is defined as the last measurement prior to the first dose of study drug, unless otherwise stated.

3.1.4 Summary Statistics

Categorical data will generally be summarized with counts and percentages of subjects. The denominator used for the percentage calculation will be clearly defined. Continuous data will generally be summarized with descriptive statistics including n (number of non-missing values), mean, median, standard deviation, 1st and 3rd quartiles, minimum, and maximum.

3.1.5 Hypothesis Testing

The percentage change in LDL-C from Baseline to Day 84 for each treatment group is defined mathematically as μ_j , where j stands for the jth treatment (j=0,1,2,3) and the subscript 0 refers to the placebo, 1 refers to obicetrapib 10 mg monotherapy, 2 refers to ezetimibe 10 mg monotherapy, and 3 refers to the FDC treatment group. The hypothesis testing to the percent change in LDL-C from Baseline to Day 84 is then defined statistically as following:

$$H_0$$
: μ_3 - μ_j = 0 (where j=0,1,2) and μ_1 - μ_0 = 0

$$H_1$$
: μ_3 - $\mu_i \neq 0$ (where j=0,1,2) and μ_1 - $\mu_0 \neq 0$.

Each of the comparisons within the co-primary endpoint family will be conducted at a significance level of 0.05. If and only if all 4 testing achieve statistical significance, the study is claimed to meet its primary objective and the hypothesis testing will continue to secondary endpoints, otherwise all statistical comparisons for secondary endpoints are considered descriptive only.

3.1.6 Evaluation of Site Effect

This is a multi-center study. Sites will not be pooled for any planned inferential analysis but may be pooled for subgroup analysis to assess the heterogeneity of treatment effects among pooled sites. The final pooling algorithm, if needed, will be specified before treatment unblinding and will be provided as an addendum to the SAP. Additionally, a review of by-site effects will be performed in the context of data listing review.

3.1.7 Handling of Dropouts and Missing Data

The objective is for missing data to be kept to a minimum. Continued efforts will be made to measure endpoints on all subjects, including those who may have discontinued study drug. Accordingly, site investigators have been robustly trained about the importance of participant retention and multiple approaches will be implemented to retain participants who fail to actively maintain contact with the investigator.

Date Values

In cases of incomplete dates (e.g., AE, concomitant medication, and medical history start and/or stop dates), the missing component(s) will be assumed as the most conservative value possible. For example, if the start date is incomplete, the first day of the month will be imputed for the missing day and January will be imputed for the missing month. If a stop date is incomplete, the last day of the month will be imputed for the missing day and December will be imputed for the missing month. Incomplete start and stop dates will be listed as collected without imputation.

Date imputation will only be used for computational purposes such as treatment-emergent status. Actual date values, as they appear in the original CRFs, will be presented within the data listings.

Non-Date Values

For the primary efficacy endpoint, missing values will be imputed using multiple imputation methods (see Section 3.4.1). For the analyses of secondary and exploratory efficacy endpoints, no imputation will be made for missing values. Safety data will be used according to availability, with no imputation for missing data.

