8.1 Adverse Events

An AE is defined as any untoward medical occurrence in a clinical investigation participant administered a pharmaceutical product, which does not necessarily have a causal relationship with this treatment. An AE can therefore be any unfavorable and/or unintended sign (including a clinically significant abnormal laboratory finding), symptom, or disease temporally associated with the use of an investigational medicinal product (IMP), whether or not related to the IMP. All AEs, including observed or volunteered problems, complaints, or symptoms, are to be recorded on the appropriate eCRF.

AEs, which include clinical laboratory assessment variables, will be monitored and documented from the time of first dose of study treatment until completion of Visit 5 (Day 112). Participants should be instructed to report any AE that they experience to the Investigator, whether or not they think the event is due to a study drug. Beginning at the date of the first dose of study treatment, Investigators should make an assessment for AEs at each visit and record the event on the appropriate AE eCRF.

Wherever possible, a specific disease or syndrome rather than individual associated signs and symptoms should be identified by the Investigator and recorded on the eCRF. However, if an observed or reported sign or symptom is not considered a component of a specific disease or syndrome by the Investigator, it should be recorded as a separate AE on the eCRF. Additionally, the condition that led to a medical or surgical procedure (eg, surgery, endoscopy, tooth extraction, or transfusion) should be recorded as an AE, not the procedure itself.

Any medical condition already present at the date of the first dose of study treatment should be recorded as medical history and not be reported as an AE unless the medical condition or signs or symptoms present at baseline changes in severity, frequency, or seriousness at any time during the study. In this case, it should be reported as an AE.

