3 STATISTICAL METHODOLOGY

3.1 General Considerations

3.1.1 Analysis Day

Analysis day will be calculated from the date of first dose of study drug. The day of the first dose of study drug will be Day 1, and the day immediately before Day 1 will be Day -1. There will be no Day 0.

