3.5.1 Adverse Events (AEs)

AEs will be categorized by primary system organ class and preferred term as coded using the current MedDRA version category designation.

An overview of treatment-emergent AEs (TEAEs) will be provided including counts and percentages of participants with the following:

- Any TEAEs (overall and by maximum severity)
- Any TEAEs (non-serious)
- Any study drug related TEAEs (overall and by maximum severity)
- Any TEAEs leading to discontinuation of study drug
- Any drug related TEAEs leading to discontinuation of study drug
- Any treatment-emergent serious AEs (TESAEs)
- Any study drug related TESAEs
- Any TEAEs leading to death.

The TEAEs described above will be summarized separately by system organ class and preferred term. The non-serious TEAEs occurring in more than 2% of participants in any treatment group and preferred term will be summarized.

Listings will be presented specifically for TEAEs, TESAEs, TEAEs leading to discontinuation of study drug, and TEAEs leading to death.

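### The SAP's rule for incomplete AE start dates has no floor at first dose, so some on-treatment AEs with partial dates would be classed as pre-treatment

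*SAP*

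**What the plan says.** SAP 3.1.7 (Date Values) treats AE, concomitant medication and medical history dates together. Its principle is that "the missing component(s) will be assumed as the most conservative value possible". The rule it then gives for start dates is that "if the start date is incomplete, the first day of the month will be imputed for the missing day and January will be imputed" for a missing month. The purpose is stated: "Date imputation will only be used for computational purposes such as treatment-emergent status". The section sets no lower bound at the first-dose date and no default for an AE whose timing is ambiguous.

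SAP 3.1.1 fixes the time origin: "The day of the first dose of study drug will be Day 1, and the day immediately before Day 1 will be Day -1".

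SAP 3.5.1 builds its AE reporting on treatment-emergent events: "An overview of treatment-emergent AEs (TEAEs) will be provided including counts and percentages of participants with the following", and "The TEAEs described above will be summarized separately by system organ class and preferred term". The listings it names are also for TEAEs and TESAEs. The section plans no table of all AEs. TEAE is spelled out in the abbreviation list but defined nowhere.

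Protocol 8.1 limits what reaches the AE form. AEs "will be monitored and documented from the time of first dose of study treatment until completion of Visit 5 (Day 112". On earlier conditions it says: "Any medical condition already present at the date of the first dose of study treatment should be recorded as medical history", with an exception for conditions that change in severity, frequency or seriousness during the study.

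**The concern.** The earliest possible date is a cautious choice for the start of a medication or of a past illness. For treatment-emergent status it is the least cautious choice, because it pushes an ambiguous event to before first dose. The rule therefore works against the principle it is meant to illustrate.

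It also works against the collection rule. Protocol 8.1 opens AE recording at first dose, so a new AE that the imputation places before first dose is normally an artefact of the imputation.

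The error runs in one direction only, towards undercounting, and it falls mainly on the first weeks of dosing, when the AE and the first dose most often share a calendar month. AE incidence is one of the safety endpoints in SAP 2.3.4, and the affected events would be missing from the tables that report it.

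**Working it through.** The documents give no figure on this point, so there is nothing to reproduce.

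**Inputs from the documents**
- Missing day becomes the 1st; missing month becomes January; no floor (SAP 3.1.7).
- Day 1 is the date of first dose (SAP 3.1.1).
- AEs are collected from first dose to Day 112 (Protocol 8.1).

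**Assumptions**
- A TEAE is an AE with a start date on or after first dose.
- First-dose dates are spread evenly over a 365-day year.
- Where the month is missing, the day is missing too, so the imputed date is 1 January.
- Onset patterns: uniform over 112 days, uniform over the first 28 days, or exponential with mean 28 days within the 112 days.

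**Worked example, first dose on 14 March**
- AE dated March, no day: imputed 1 March, before first dose. Wrong.
- AE dated April, no day: imputed 1 April, after first dose. Right.
- AE with only the same year known: imputed 1 January, before first dose. Wrong.

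**Missing day, onset uniform over 112 days.** In a month of L days with first dose on day d, there are L − d + 1 possible onset days left in that month. All are misclassified unless d = 1. Summing over d = 2 to L gives L(L − 1)/2.
- Seven 31-day months: 7 × 465 = 3,255
- Four 30-day months: 4 × 435 = 1,740
- February: 378
- Total 5,373, out of 365 × 112 = 40,880 pairs of first-dose date and onset day: 5,373/40,880 = 13.1%

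Pairs within the first-dose month, including first dose on the 1st, number 7 × 496 + 4 × 465 + 406 = 5,738. So 5,373/5,738 = 94% of AEs in that month are misclassified. In later months it is 0%.

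**Missing day, onset uniform over the first 28 days.** The same sum, with at most 28 onset days per first-dose date: 7 × 462 + 4 × 434 + 378 = 5,348, out of 365 × 28 = 10,220: 52.3%.

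**Missing month, onset uniform over N days.** The AE is misclassified if it falls in the first-dose year and first dose was not on 1 January. The share is 1 − (N + 1)/(2 × 365).
- N = 112: 1 − 113/730 = 84.5%
- N = 28: 1 − 29/730 = 96.0%

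A day-by-day enumeration gives the same values and adds the exponential pattern:

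| Onset pattern | Day missing | Month missing |
|---|---|---|
| Uniform, Days 1-112 | 13% | 85% |
| Exponential, mean 28 days | 39% | 93% |
| Uniform, first 28 days | 52% | 96% |

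Complete dates are never affected. If the imputed date is set no earlier than first dose whenever the known parts are compatible with the first-dose month or year, every cell becomes 0%.

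**The case against.** **The rule is only an example.** The first-of-month and January values follow a general principle of conservatism, which for AEs would favour counting the event. SAP 6 also leaves programming detail to a separate document. Both are true, but the example is the only operational rule in the SAP and the one a programmer would code. The conflict between rule and principle remains.

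**TEAE is undefined.** If it meant any event on the AE form, nothing would be lost. That reading is possible, but SAP 3.1.7 says that imputed dates determine treatment-emergent status, which points the other way. The missing definition is itself a reason to amend.

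**Partial dates should be rare.** AEs are assessed at each visit of a 16-week study, missing data are queried to the site (Protocol 10.1.5), and an eCRF is complete only when missing data are accounted for (Protocol 10.1.1). This stands: the percentages apply to a denominator that is unknown and probably small.

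**The consequence is limited.** Safety is descriptive (SAP 3.5) and the rule is the same in all four arms. This stands too.

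A reader might also infer that on-treatment AEs with incomplete dates generally vanish from every AE table. The documents do not support that. A missing day in a later month, or a missing month in the year after first dose, is classed correctly. SAP 3.5.2 summarises new-onset diabetes and macular degeneration cases without limiting them to TEAEs. SAP 3.3.1 tabulates the primary reasons for stopping treatment, and SAP 6 lists all available data, with dates shown as recorded. Nor do the documents show that serious AEs would be lost in practice: Protocol 8.3 requires a dedicated report within 24 hours of awareness, and nothing suggests that such reports lack a start month or day.

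**Conclusion.** The concern holds in a limited form. Followed as written, SAP 3.1.7 classes an on-treatment AE as pre-treatment if its day is missing and onset is in the first-dose month (unless first dose was on the 1st), or if its month is missing and onset is in the first-dose year (unless first dose was on 1 January). The event then leaves the SAP 3.5.1 summaries and named listings.

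The size is conditional on the date being partial: 13% to 52% of AEs with a missing day and about 85% to 96% of those with a missing month, depending on how early onsets cluster. These figures rest on the assumed TEAE definition and on evenly spread first-dose dates. The absolute number of affected AEs cannot be computed from the documents. No efficacy result, error rate or power figure is touched. This is a minor correction to a rule that is wrong as written, and it does not threaten the trial's conclusions.

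**What to change.** Amend SAP 3.1.7 and 3.5.1 before unblinding:

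1. Define TEAE explicitly, for example as an AE with a start date on or after the first dose of study drug.
2. Treat an AE with an incomplete start date as treatment-emergent unless the known date parts or the stop date show that it began before first dose.
3. For such AEs, where the known parts are compatible with the first-dose month (day missing) or the first-dose year (month missing), impute the first-dose date. Otherwise keep the first-of-month and January rule.
4. Leave the present rule for medication and medical history dates.

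The cost is a definition and a sentence or two in the SAP, and a small change in the AE derivation. TEAE counts may rise slightly. Made before unblinding, the change is neutral between arms; reclassifying AEs once assignments are known would be harder to defend.

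The same edit could state whether imputed AE start dates also feed the 30-day antihypertensive medication window in SAP 3.5.2, which the SAP leaves open.

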4.5 Withdrawal Criteria

A participant may prematurely discontinue study drug and/or withdraw from the study at any time. However, a distinction must be made between premature discontinuation of study drug and withdrawal from the study. All efforts should be made to ensure the participant continues in the study per protocol. If a participant discontinues study drug prior to completion of the study, all efforts will be made to continue to follow the participant and collect data for all visits.

Only participants that request discontinuation from the study and withdraw consent will be considered withdrawn from the study. For safety reasons, it will be recommended that all participants who withdraw from the study complete an End of Treatment (EOT) Visit. Withdrawn participants will not be replaced.

Participants may need to discontinue study drug during the course of the study. All efforts will be made to restart the study drug; however, in the event of the following, participants may be permanently discontinued from study drug:

- Occurrence of any medical condition or circumstance that exposes the participant to substantial risk and/or does not allow the participant to adhere to the protocol-specified study drug treatment regimen;
- Any SAE, clinically significant AE, severe laboratory abnormality, intercurrent illness, or other medical condition, which indicates to the Investigator that continued treatment with study drug is not in the best interest of the participant;
- Pregnancy; or
- Requirement of prohibited concomitant medication.

If a participant permanently discontinues study drug, he/she will continue to participate in study visits as described below:

- If a participant discontinues study drug between Visit 2 (Day 1) and Visit 3 (Day 28) or at Visit 3 (Day 28), he/she should complete an EOT Visit at Day 28, return to complete Visit 4 (Day 84), and return to complete the Safety Follow-up Visit (Day 112); or
- If a participant discontinues study drug between Visit 3 (Day 28) and Visit 4 (Day 84), he/she should return for Visit 4 (Day 84) and the Safety Follow-up Visit (Day 112) as scheduled.

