9.2.1.2 Secondary efficacy analyses

In order to control the Type I error rate, a fixed sequential testing procedure will be implemented. In a hierarchical step-down manner, the co-primary endpoints will be tested first, followed by the secondary efficacy endpoints in the order specified. Continuous secondary efficacy endpoints will be analyzed using similar methods as in the primary efficacy analysis.

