3.4 Efficacy Assessment

The ITT Population will be the primary population for the efficacy analysis. Efficacy will also be analyzed using the FAS, the mITT Population, mITT On-Treatment Population, and PP Population as supportive analyses. Primary and secondary efficacy endpoints will be presented in listings.

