class TREATMENT;
modeleffects TREATMENT;
ods output parameterestimates=mi_LSM;
proc mianalyze parms(classvar=full)=mixDIFF;
class TREATMENT;
modeleffects TREATMENT:
ods output parameterestimates=minus_mi_DIFF;
```

The first sensitivity analysis will be performed imputing missing LDL-C values at Day 84 based on the assumption the data are MNAR using a control-based pattern mixture method. At Day 84, the data will be split into two groups as follows: (1) all participants randomized to the obicetrapib 10 mg + ezetimibe 10 mg FDC treatment, ezetimibe 10 mg monotherapy, and obicetrapib 10 mg monotherapy treatment groups that had a non-missing value at Day 84; and (2) either participants randomized to the placebo treatment group, or participants that had a missing value at Day 84. For the second group, 100 data sets will be imputed. The variables for the imputation model will consist of the LDL-C values from Baseline and Day 84. In this manner, missing data at the Day 84 assessment will be estimated from the placebo treatment group. Each data set will be combined with the first group to obtain 100 imputed data sets with no missing values at Day 84. For each imputation data set, the percent change from baseline to Day 84 will be analyzed using the ANCOVA model described above. The results of these 100 analyses will be combined to construct the treatment estimates using the parameter estimates and associated standard errors. Similarly, the difference of the adjusted treatment means will be presented with the associated standard error and two-sided 95% confidence interval. Randomly chosen seed numbers will be selected for the analysis and will be retained.

The second sensitivity analysis will be performed using the ANCOVA model from the primary analysis for the ITT Population using only observed cases with no imputation for missing data.

The third sensitivity analysis will be performed using ANCOVA model from the primary analysis for the ITT Population using the last observation carried forward (LOCF), i.e. if the Day 84 measurement is missing, then the last on-treatment measurement will be used.

Supplemental Analyses

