Supplemental analyses will be performed for the primary efficacy endpoint in order to assess any differences with the results from the primary analysis and investigate what effect, if any, protocol violations have on the trial results. In the first supplemental analysis, a mixed model for repeated measures (MMRM) approach will be utilized. The analysis will include fixed effects for treatment group, visit, and treatment-by-visit interaction, along with covariates of the Baseline LDL-C value as a continuous covariate. The restricted maximum likelihood estimation approach will be used with an unstructured covariance matrix. The LS mean, standard errors, and 2-sided 95% confidence intervals for the treatment group and for the comparison of the treatment groups (FDC treatment vs. placebo, FDC treatment vs. ezetimibe 10 mg, and FDC treatment vs. obicetrapib 10 mg, and obicetrapib 10 mg vs. placebo) will be provided. The MMRM approach will include all available assessments of percent change in LDLC from Day 1, Day 28, and Day 84. The model assumes that the data are missing at random (MAR). If any data are missing, the model will use all information from the other time points to estimate the mean treatment difference at the given time point. No imputation of missing data will be performed. The analysis will be conducted for ITT Population.

Additional supplementary analysis will be performed using the ANCOVA model from the primary analysis based on the FAS, mITT, mITT On-Treatment, and PP populations. No imputation for missing data will be performed for the analysis.

Secondary Estimand

A secondary estimand will be assessed for the primary efficacy endpoint. The secondary estimand is defined by the following key attributes:

- Treatment:

- obicetrapib 10 mg + ezetimibe 10 mg FDC treatment versus placebo,
 ezetimibe 10 mg monotherapy, and obicetrapib 10 mg monotherapy, and obicetrapib 10 mg monotherapy versus placebo
- Target Population: participants who are randomized into the study
- Analysis Population: The ITT Population
- **Intercurrent events**: treatment discontinuation, prohibited medication use
- Analysis set and handling of intercurrent events: A hypothetical strategy will be used. All available values of LDL-C at Baseline and Day 84 will be included in the calculation of the percentage change from Baseline to Day 84.

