3.4.2 Secondary Efficacy Endpoints

Similar ANCOVA models as described for the primary analyses will be used to analyze the secondary efficacy endpoints and will be tested sequentially at the 0.05 significant level according to the order specified below, if all 3 co-primary endpoints achieved statistical significance. Otherwise, all statistical comparisons for secondary endpoints are considered descriptive only:

- Percent change from Day 1 to Day 84 in non-HDL-C for the obicetrapib 10 mg + ezetimibe 10 mg FDC treatment group compared with the placebo group;
- Percent change from Day 1 to Day 84 in ApoB for the obicetrapib 10 mg + ezetimibe 10 mg FDC treatment group compared with the placebo group;
- Percent change from Day 1 to Day 84 in non-HDL-C for the obicetrapib 10 mg monotherapy treatment group compared with the placebo group;
- Percent change from Day 1 to Day 84 in ApoB for the obicetrapib 10 mg monotherapy compared with the placebo group;

- Percent change from Day 1 to Day 84 in non-HDL-C for the obicetrapib 10 mg + ezetimibe 10 mg FDC treatment group compared with the ezetimibe 10 mg monotherapy treatment group;
- Percent change from Day 1 to Day 84 in ApoB for the obicetrapib 10 mg + ezetimibe 10 mg FDC treatment group compared with the ezetimibe 10 mg monotherapy treatment group;
- Percent change from Day 1 to Day 84 in non-HDL-C for the obicetrapib 10 mg + ezetimibe 10 mg FDC treatment group compared with the obicetrapib 10 mg monotherapy treatment group; and
- Percent change from Day 1 to Day 84 in ApoB for the obicetrapib 10 mg + ezetimibe 10 mg FDC treatment group compared with the obicetrapib 10 mg monotherapy treatment group.

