5 CHANGES FROM PROTOCOL-SPECIFIED STATISTICAL ANALYSES

There has been one change from the protocol v3.0:

• The inclusion of subgroup analysis.

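### The eight ranked secondary endpoints are analysed on observed cases only, a method the SAP treats as a sensitivity analysis for LDL-C, with no estimand and no missing-data sensitivity analysis of their own

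*SAP*

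**What the plan says.** **Primary endpoint.** SAP 3.4.1 gives LDL-C a treatment-policy estimand. Missing Day 84 values are multiply imputed under a missing-not-at-random assumption, using participants in the same arm who stopped drug but were still measured. If there are too few of these for the model to work, imputation from the placebo arm takes over. Three sensitivity analyses follow: placebo-based imputation, the same ANCOVA "for the ITT Population using only observed cases with no imputation for missing data", and last observation carried forward. A hypothetical estimand is added as well: "A secondary estimand will be assessed for the primary efficacy endpoint".

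**Secondary endpoints.** SAP 3.4.2 lists eight, tested in order at 0.05: non-HDL-C and ApoB, each for FDC versus placebo, obicetrapib versus placebo, FDC versus ezetimibe and FDC versus obicetrapib. On method it says "Similar ANCOVA models as described for the primary analyses will be used to analyze the secondary efficacy endpoints". On missing data, SAP 3.1.7 says "For the analyses of secondary and exploratory efficacy endpoints, no imputation will be made for missing values". SAP 3.4 adds "The ITT Population will be the primary population for the efficacy analysis".

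**Protocol.** Section 9.2.1.2 says "Continuous secondary efficacy endpoints will be analyzed using similar methods as in the primary efficacy analysis". The multiple imputation is described in section 9.2.1.1 under the primary efficacy analysis. SAP section 5 states "There has been one change from the protocol v3.0", namely the subgroup analysis.

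**The concern.** ANCOVA without imputation can use only participants with both a baseline and a Day 84 value, so the intention-to-treat label does not keep the others in the analysis. Observed-case ANCOVA in effect treats a participant with no Day 84 value like an observed participant in the same arm with the same baseline. The primary analysis of LDL-C declines to make that assumption.

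Non-HDL-C and ApoB belong to the same fasting lipid profile as LDL-C and are drawn at the same visits (Protocol Appendices A and B). One missed Day 84 visit is therefore handled as missing not at random for LDL-C and by exclusion for the other two, and the SAP gives no reason. The testing sequence changes its missing-data assumption as it passes from the co-primary to the secondary endpoints. The secondary endpoints have no stated estimand and no analysis that varies the assumption. The supportive populations in SAP 3.4 do not fill this gap, because the no-imputation rule applies there too.

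**Working it through.** **1. What the text requires.** SAP 3.4.2 read alone might be taken to carry the imputation along with the ANCOVA model. SAP 3.1.7 rules that out expressly. The main secondary analysis is therefore ITT, ANCOVA, observed cases, which for LDL-C is the second sensitivity analysis.

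**2. Who is lost.** Participants who stop drug are still followed: "If a participant discontinues study drug prior to completion of the study, all efforts will be made to continue to follow the participant" (Protocol 4.5). Nothing excludes their Day 84 values. Early-termination visits on Days 57 to 98 are also mapped to Day 84 (SAP 3.1.2). Only values that are truly absent are affected. At the planned dropout of about 5% of 100 per arm, that is about 5 participants per arm.

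**3. The plan's own power figures (SAP 2.2.2).** Inputs: 95 evaluable per arm, SD 25, one-sided 0.025, LDL-C differences of 30, 20, 15 and 12 points. Power = Φ(d / (SD√(2/n)) − 1.96). For d = 12, the standard error is 25√(2/95) = 3.63 and 12/3.63 = 3.31, so power is Φ(1.35) = 91.1% (90.8% with the noncentral t). The others are 98.5% (15), 99.98% (20) and above 99.9% (30). Enrolment is 95/0.95 = 100 per arm, or 380/0.95 = 400 in all. The plan's figures reproduce.

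**4. Illustrated shift in the estimate.** The documents give no effect or SD for non-HDL-C or ApoB, so the LDL-C values stand in. Assume a fraction m is missing equally in every arm.

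- Participants with no Day 84 value keep none of the effect (the assumption of the placebo-based fallback): difference = (1 − m)d.
- They keep half of it (assumed): difference = (1 − 0.5m)d.
- Observed cases still estimate d.

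| d | m = 5%, none kept | m = 10%, none kept | m = 5%, half kept | m = 10%, half kept |
|---|---|---|---|---|
| 30 | 28.5 | 27.0 | 29.25 | 28.5 |
| 20 | 19.0 | 18.0 | 19.5 | 19.0 |
| 15 | 14.25 | 13.5 | 14.625 | 14.25 |
| 12 | 11.4 | 10.8 | 11.7 | 11.4 |

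With none kept, the gap at 5% is 0.6 to 1.5 points. Over m = 2% to 15% it is 0.24 to 1.8 points for d = 12 and 0.6 to 4.5 points for d = 30. The planned retrieved-dropout model would probably give a smaller gap than this.

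**5. Illustrated power for the 12-point comparison.** Observed cases, noncentral t, two-sided 0.05: 90.8% with 95 per arm and 89.3% with 90. Placebo-based multiple imputation was simulated with 100 per arm, 2000 runs, 20 imputations, active arms assumed 15 and 27 points better than placebo, and no baseline covariate.

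| Missing | Observed cases | Placebo-based imputation |
|---|---|---|
| 5% | 91.2% | 88.4% |
| 10% | 89.1% | 82.3% |

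Monte Carlo error is about 0.6 to 0.9 percentage points. As a rough check, a true difference of 11.4 with 100 per arm gives 89.7% before any variance is added for imputation.

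**The case against.** The best defence is that the rule is stated openly and in advance. Protocol 9.2.1.1 ties imputation to the primary analysis, and the wording of 9.2.1.2 can be read as meaning the ANCOVA model only. On that reading nothing departs from the protocol and SAP section 5 had nothing to list. This stands: the silence of section 5 is a fault only if the protocol wording covers imputation. It does not explain why the two sets of endpoints are handled differently.

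The LDL-C sensitivity analyses would also show how much missingness matters in largely the same participants. That is useful but indirect, because it gives no figure for non-HDL-C or ApoB.

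Three points on size are fair:

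- With equal missingness and no true effect, both methods estimate zero, so no inflation of Type I error is shown.
- The figures above use the fallback at full loss, not the planned retrieved-dropout model.
- Part of the simulated power loss comes from conservative pooled variance. In null runs, placebo-based imputation rejected about 4.6% of the time at 5% missing and 3.5% at 10%, against a nominal 5%.

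Finally, with about 5 participants lost per arm, measured dropouts to impute from may also be few. SAP 3.4.1 foresees this for LDL-C, and its fallback would carry over.

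**Conclusion.** The concern holds. Eight endpoints under Type I error control have as their main analysis what the SAP gives LDL-C only as a sensitivity check. They have no stated estimand and no analysis that tests the missing-data assumption.

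The effect is small at the planned dropout rate. It is at most 0.6 points on a 12-point difference and 1.5 on a 30-point one, if LDL-C planning values carry over, missingness is equal across arms and the missing participants keep none of the effect. It grows in proportion to missingness. Missingness that differs by arm was not modelled. The sample size and the LDL-C conclusions are not affected.

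**What to change.** In SAP 3.1.7 and 3.4.2, apply the primary multiple imputation to the eight ranked endpoints. Use each analyte's own baseline and Day 84 values, with the same donor groups and the same placebo-based fallback. State that these endpoints follow the same treatment-policy estimand, and keep observed-case ANCOVA as their sensitivity analysis.

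If the no-imputation rule is kept, give the reason in 3.4.2, record it in section 5, and add the primary imputation as a sensitivity analysis for these endpoints. Either change belongs in the SAP before database lock.

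The cost is low. The imputation code is re-used for two analytes already collected at the same visits. Estimates may become slightly less favourable. A 12-point comparison would lose about 3 points of power at 5% missing in the full-loss case. Reliance on a small number of measured dropouts would extend to two more analytes.
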